### Subject Selection

Inclusion criteria:

- At least 18 years of age
- Admitted to the intensive care services at MGH, SCGH, or BIDMC
- Requiring IV vasopressors at a rate of less than 100 mcg/min of phenylephrine, or 8 mcg/min of norepinephrine, or metaraminol 60mcg/min and unable to wean for more than 24 hours while still maintaining desired blood pressure goals.

Exclusion criteria:

- Clinical evidence of inadequate tissue oxygenation
- Clinical evidence of liver failure
- Hypovolemic shock or hypotension due to adrenal insufficiency (based on clinical suspicion or available routine testing)
- Pregnancy confirmed with a pregnancy test. Women between the ages of 18–55 who have not had a surgical hysterectomy will only be eligible for inclusion if they have a negative urine pregnancy test. Pregnancy testing will not need to be repeated if there is a documented negative urine pregnancy test that was obtained within 7 days prior to starting study drug, provided the woman was an ICU inpatient throughout that period of time.

- Chronic renal failure (serum creatinine >2mg/dL or 180 µmol/L)
- Severe organic heart disease (ejection fraction less than 30%)
- Acute urinary retention
- Pheochromocytoma (based on clinical suspicion)
- Thyrotoxicosis (based on clinical suspicion)
- Enrolment in another clinical trial
- Midodrine as pre-admission medication
- Any known allergies to midodrine
- Bradycardia (HR <50/min)
- No enteral route available

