### Outcomes

Study endpoints include the following:

- *Primary endpoint:*
  - Hours from initiation of midodrine until discontinuation of IV vasopressors
- *Secondary endpoints:*
  - ICU length of stay (LOS), hospital LOS, rates of ICU readmission
- *Safety endpoints:*
  - hypertension (increase in blood pressure to a systolic blood pressure (SBP) 20 percent higher than the predefined goal set by the primary team), bradycardia (decrease in heart rate 20 percent lower than the predefined goal set by the primary team), hemodynamically significant tachyarrhythmia (>20 percent decrease in systolic blood pressure).

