### Outcomes

- *Primary endpoint:*
  - Time until discontinuation of IV vasopressors, measured in hours from initiation of midodrine until discontinuation of IV vasopressors
- *Secondary endpoints:*
  - Time to ICU discharge readiness, defined as the number of days from study drug initiation to meeting discharge criteria
  - ICU length of stay, defined as the number of days in the ICU prior to transfer to the general floor
  - Hospital length of stay, defined as the total number of days in the hospital after first study drug administration
  - Rates of ICU readmission, defined as the number of patients readmitted back to the ICU after prior discharge to the general floor
- *Safety endpoints:*
  - Hypertension (increase in blood pressure to a systolic blood pressure (SBP) 20 percent higher than the predefined goal set by the primary team), bradycardia (decrease in heart rate 20 percent lower than the predefined goal set by the primary team), hemodynamically significant tachyarrhythmia (>20 percent decrease in systolic blood pressure).

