### Data Collection

Baseline descriptive data collection will occur on day of enrolment and includes age, sex, ethnicity, APACHE II score, admission diagnosis, pre-existing co-morbidities (diabetes, coronary artery disease, asthma, peripheral vascular disease, renal failure, psychiatric disease, musculoskeletal disease, and others) obtained from the subject, the subject's family, and the subject's medical chart. Baseline laboratory data will be recorded (haemoglobin, white cell count, alanine aminotransferase (ALT), international normalised ratio (INR), bilirubin, urea, creatinine, troponin, lactate). During the study daily SOFA scores, blood pressure goals, total fluid balances, transfused red blood cell units, administered corticosteroids, use of epidural analgesia, vasopressor and study drug start and end

times will be recorded. Days between admission and discharge from the ICU and hospital will be recorded. Readmissions to the ICU during the hospital stay will be identified through daily medical record review.

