#### *Analysis of primary and secondary outcomes*

A parametric t-test or Mann-Whitney U test will be used, as appropriate, to determine whether time from initiation of midodrine until discontinuation of IV vasopressors, time from ICU admission to ICU discharge readiness, and ICU and hospital LOS differ between groups.

A Chi-Square or Fisher's exact test will be used to test whether rates of ICU readmission and incidence of adverse events are different between treatment groups.

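### As worded, ICU length of stay has no study-drug start, so it includes pre-treatment days that midodrine cannot affect and runs on a different clock from hospital stay

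*Combined protocol and SAP*

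**What the plan says.** The SAP's Outcomes section lists three duration endpoints among the secondary endpoints:

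- The entry for discharge readiness names study drug as its start: "Time to ICU discharge readiness, defined as the number of days from study drug initiation to meeting discharge criteria".
- The entry for ICU stay names only an end, the transfer to the floor: "ICU length of stay, defined as the number of days in the ICU prior to transfer to the general floor".
- The entry for hospital stay again names study drug as its start: "Hospital length of stay, defined as the total number of days in the hospital after first study drug administration".

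The protocol's own Outcomes section does not fill the gap, because it lists "ICU length of stay (LOS), hospital LOS, rates of ICU readmission" with no time origin for either stay.

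Three other places bear on the point:

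- Protocol, Subject Selection: patients must be "unable to wean for more than 24 hours while still maintaining desired blood pressure goals" before they can enter.
- SAP, Data Collection: "Days between admission and discharge from the ICU and hospital will be recorded".
- SAP, Analysis of primary and secondary outcomes: "A parametric t-test or Mann-Whitney U test will be used, as appropriate" for the duration endpoints. No covariate adjustment is planned.

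The SAP states no expected effect, standard deviation or power for ICU length of stay.

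**The concern.** Days spent in the ICU before the first dose are fixed by the time treatment starts. Counting them adds the patient-to-patient spread of prior ICU stay to the endpoint and adds nothing to the treatment difference. Subject Selection sets a minimum period of failed weaning but no upper limit on prior ICU stay, so that spread could be wide.

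Two things are at stake. A shorter ICU stay is part of the hypothesis in the protocol's Purpose and one of its Possible Benefits, and a diluted comparison that finds nothing could be misread as evidence of no effect. The Purpose also sets ICU stay beside hospital stay (shorter ICU stay without longer hospital stay), so readers will compare the two. On different clocks they are not comparable.

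**Working it through.** **Step 1. Compare the time origins.**

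| Endpoint (SAP, Outcomes) | Start | End |
|---|---|---|
| Time to discharge readiness | study drug initiation | discharge criteria met |
| ICU length of stay | none stated | transfer to the floor |
| Hospital length of stay | first study drug administration | not spelled out; days in hospital |

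No section gives ICU length of stay a study-drug start. Its unrestricted wording covers every ICU day up to transfer.

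**Step 2. Consistency within one patient.** Take a hypothetical patient with 15 ICU days before the first dose, 2 ICU days after it, and hospital discharge 5 days after it. ICU stay is 15 + 2 = 17 days. Hospital stay is 5 days. The part exceeds the whole.

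**Step 3. Effect on precision.** The plan has no figure for this endpoint to reproduce; its sample size (50 per group, target 120) concerns the primary endpoint only. Everything below therefore rests on assumed SDs.

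Let s_post and s_pre be the SDs of ICU days after and before the first dose, with correlation ρ.

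- Variance of total stay = s_post² + s_pre² + 2ρ·s_pre·s_post
- With ρ = 0, standard-error inflation = √(1 + s_pre²/s_post²)
- Effective total N = 120 / inflation²
- 95% CI half-width for the mean difference = 1.96 × s_post × inflation × √(2/60)

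Equal SDs: inflation = √2 = 1.41 and effective N = 120/2 = 60, whatever the common SD.

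With s_post = 3 days, 60 per arm and ρ = 0, counting from first dose gives 1.96 × 3 × √(2/60) = 1.07 days. Counting all ICU days gives:

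| s_pre (days) | Inflation | Half-width (days) | Effective N |
|---|---|---|---|
| 2 | √(1 + 4/9) = 1.20 | 1.29 | 83 |
| 3 | √(1 + 9/9) = 1.41 | 1.52 | 60 |
| 5 | √(1 + 25/9) = 1.94 | 2.09 | 32 |
| 7 | √(1 + 49/9) = 2.54 | 2.73 | 19 |

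**Step 4. The same point as power.** Assume 50 per arm, a true 1-day difference, s_post = 2 days and two-sided 0.05 (normal approximation). Counting from first dose, power is about 0.71. Counting all ICU days:

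| s_pre (days) | Power, ρ = 0 | Power, ρ = 0.3 | Multiplier on n, ρ = 0 |
|---|---|---|---|
| 1 | 0.61 | 0.52 | 1.25 |
| 2 | 0.42 | 0.34 | 2.0 |
| 4 | 0.20 | 0.17 | 5.0 |

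**Step 5. Does the direction depend on ρ = 0?** Total stay is more variable than post-dose stay unless ρ is below −s_pre/(2·s_post), which is −0.5 for equal SDs. Positive correlation makes the loss larger.

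**The case against.** Several points can fairly be made against this.

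- **The SAP does not say that ICU stay is counted from ICU admission.** Correct. A reader might infer that it does, and might take the Data Collection sentence as confirmation. That sentence covers ICU and hospital stay alike, yet hospital stay is analysed from first dose. It describes what is captured and does not set the analysis clock. What stands is that no start is stated and that the unrestricted wording includes pre-dose days.
- **Randomisation balances prior stay.** On average it does, so a reader who infers bias goes too far. A chance imbalance in prior stay would shift the observed difference, but that is already part of the sampling variance in the working and is not a second harm.
- **The size is assumed.** It is. The documents give no SD, correlation or distribution of prior ICU stay. A minimum common to all patients adds no variance; only the spread does. The working uses mean differences, while the SAP also allows a Mann-Whitney U test, and 60 per arm ignores drop-out. The inflation factor itself does not depend on the number per arm.
- **The 6-hour effect invites comparison with these intervals.** It belongs to the primary endpoint. The documents state no effect on ICU stay, so the comparison has no basis and is not made here.
- **Total ICU stay is a legitimate resource measure, and discharge readiness already supplies a drug-anchored ICU endpoint.** Total stay is worth describing. But the analysis section gives discharge readiness a different origin, listing "time from ICU admission to ICU discharge readiness, and ICU and hospital LOS differ between groups". That conflict is a separate matter, and resolving it would leave the definition of ICU stay unchanged.
- **The endpoint is exploratory.** Yes, under the SAP's multiple-comparisons statement. That limits the weight of the point without justifying the definition.

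**Conclusion.** The point holds as one of precision and comparability. As worded, ICU length of stay includes pre-treatment days, its two neighbours in the list do not, and the planned tests do nothing to remove the added variation.

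The size cannot be fixed from the documents. With independent components and equal SDs the standard error is 1.41 times what it need be; across the assumed pre-dose SDs of 2 to 7 days against a post-dose SD of 3, the factor runs from 1.20 to 2.54. The direction is safe unless pre-dose and post-dose days are strongly negatively correlated. The different clocks for ICU and hospital stay need no assumption about SDs.

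The primary endpoint starts at drug initiation and is not touched. Nothing here shows a biased comparison, or an SAP that explicitly starts the ICU clock at admission. The change should be made, but the trial's main conclusion does not depend on it.

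**What to change.** In the SAP's Outcomes section, define ICU length of stay as days from first study drug administration to ICU discharge, matching hospital length of stay. Everyone in the modified intention-to-treat population has had at least one dose, so the start is defined for every analysed patient. Add ICU days before the first dose to the baseline characteristics, and keep total ICU stay as a descriptive line for resource use.

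The cost is small but not nil. Study drug start times are already to be recorded. However, the protocol's Confidentiality and Security section keeps dates out of REDCap, and Data Collection refers to days between ICU admission and discharge. Sites may therefore have to derive the interval from first dose to ICU discharge from source records and enter it as a duration. Hospital stay from first dose already calls for a similar derivation. No new patient assessment is needed.

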### Study Procedures

Prior to randomisation, if subjects are eligible based on inclusion/exclusion criteria, informed consent will be obtained from participants. Once informed consent is obtained, the following information will be collected from the subject's medical record: demographics, past medical/surgical history, preadmission medication list, severity of illness at time of admission, blood pressure, aspartate aminotransferase, alanine aminotransferase creatinine, troponin, cortisol level.

The study drug or placebo will be selected based on the randomisation scheme and prepared by investigational pharmacists. All study personnel will be blinded, except the investigational pharmacist, to the treatment group of the subject. Subjects will be randomised to receive either 20 mg PO every 8 hours of midodrine, or placebo PO every 8 hours.

The study drug will be delivered in a double-blinded manner until:

- ICU discharge
- Rate of phenylephrine exceeds 100 mcg/min, or rate of norepinephrine exceeds 8 mcg/min, or rate of metaraminol exceeds 60mcg/min
- Subject exhibits signs and symptoms of organ failure or hypoperfusion
- Serious allergic adverse event related to midodrine
- Epinephrine requirement
- Death

If the blood pressure goal is met for more than 24 hours without IV vasopressors and the attending physician determines that the study drug is no longer required, the study drug may be discontinued at the discretion of the treating physician.

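### Bradycardia is scored against a heart-rate goal that the plan neither establishes nor lists as collected

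*Combined protocol and SAP*

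**What the plan says.** The Outcomes sections of the protocol and of the SAP give the same bradycardia endpoint: "bradycardia (decrease in heart rate 20 percent lower than the predefined goal set by the primary team". The hypertension endpoint beside it has the same form: "Hypertension (increase in blood pressure to a systolic blood pressure (SBP) 20 percent higher than the predefined goal set by the primary team".

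Two places describe the data to be collected. Protocol, Study Procedures, lists items taken from the medical record after consent, among them "severity of illness at time of admission, blood pressure, aspartate aminotransferase". SAP, Data Collection, lists what is recorded on study: "During the study daily SOFA scores, blood pressure goals, total fluid balances, transfused red blood cell units", followed by further items such as steroids and vasopressor times. Neither list names heart rate or a heart-rate goal.

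The term also appears among the exclusion criteria in Protocol, Subject Selection: "Bradycardia (HR <50/min". Protocol, Adverse Event Reporting, names bradycardia and hypertension among four pre-specified adverse events, without thresholds. The SAP section on the analysis of primary and secondary outcomes compares adverse-event incidence between arms by chi-square or Fisher's exact test.

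**The concern.** An event defined relative to a goal needs two recorded values per patient: the goal and the measurement. For bradycardia the plan lists neither. A patient with no heart-rate goal could be counted as an event, counted as a non-event, or left out of the denominator, and the plan does not say which. The SAP's Missing data section does not settle it, because its exclusion rule covers primary and secondary outcome variables only.

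Bradycardia is one of the risks of midodrine that the protocol itself names, and the protocol's section on benefits says the study should help show whether the drug is safe. If sites in two countries fill the gap in different ways, the bradycardia rate has no single meaning and is hard to interpret, whatever the test shows.

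**Working it through.** The plan states no safety rate or safety power, so there is no figure to reproduce. The check compares sections and then works out what the rule implies.

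**1. Which goals does the plan establish?**
- Protocol, Subject Selection: "unable to wean for more than 24 hours while still maintaining desired blood pressure goals". This is a blood pressure goal.
- Protocol, Study Procedures, on stopping study drug: a blood pressure goal.
- SAP, Data Collection: blood pressure goals.
- Outcomes, bradycardia: a heart-rate goal, mentioned here and nowhere else.

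**2. What threshold follows if a heart-rate goal exists?** Threshold = 0.80 × goal. The goals below are assumed, since the documents give none.

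| Assumed goal (/min) | Event threshold (/min) |
|---|---|
| 60 | 48 |
| 62.5 | 50 |
| 70 | 56 |
| 80 | 64 |
| 90 | 72 |
| 100 | 80 |

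A rate of 60/min lies below the limit for a patient with a goal of 80 and above it for a patient with a goal of 70.

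**3. How does this relate to the entry limit?** Setting 0.80 × goal = 50 gives goal = 50/0.80 = 62.5/min. Above that goal, some heart rates pass the exclusion criterion yet lie below the event limit. With a goal of 80, a patient who enters at 60/min is eligible (60 is not below 50) and is already below 64. The endpoint speaks of a decrease but names no baseline, so it is unclear whether that patient counts.

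**4. Does hypertension fail in the same way?** No. The goal is on the data list, and threshold = 1.20 × goal can be computed when the goal is systolic. Assumed systolic goals of 90, 100, 120 and 140 mmHg give 108, 120, 144 and 168 mmHg. Two details are open: the recorded goal is not said to be systolic, and on-study systolic values are not on the SAP list. If a goal were a mean pressure of 65 mmHg (assumed), applying the rule literally would flag systolic values above 1.20 × 65 = 78 mmHg.

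**The case against.** The strongest reply is that the SAP list is a summary and not the case report form, which the protocol mentions separately and which is not available here. Bradycardia is recorded as a pre-specified adverse event, study personnel assess patients daily, and a data safety monitoring board reviews adverse-event reports. This stands in part: the documents support only that the items are not listed as collected, not that they are not collected. It does not supply the threshold, because no section establishes a heart-rate goal, and the adverse-event section gives no limit of its own.

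It can also be said that a patient-specific threshold is the design and not a mistake. For blood pressure that is fair: in patients titrated to an individual goal, overshoot of that goal is a legitimate measure. For heart rate it holds only where a goal exists.

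A reader might infer three stronger points, and the documents support none of them:
- **That the 50/min figure is a competing endpoint definition.** It appears once, as an exclusion criterion, and an entry limit may differ from an on-study event limit. The two Outcomes sections agree with each other.
- **That hypertension cannot be scored either.** Blood pressure goals are recorded, so it can be scored whenever the goal is systolic.
- **That one arm would collect more false events, or that the whole safety conclusion falls.** The trial is double-blind, nothing suggests that goals would differ by arm, and tachyarrhythmia, new organ failure and serious adverse events remain as safety data.

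**Conclusion.** The point holds for bradycardia. The stated rule depends on a reference value that the plan does not establish and, like heart rate itself, does not list as collected. It therefore gives no result for a patient without a heart-rate goal. Where a goal above 62.5/min exists, the event limit overlaps with heart rates allowed at entry.

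The number of patients without a goal, and the number of events misclassified, cannot be derived: anything from none to all of the 120 planned subjects is compatible with the text. The thresholds worked out above rest on assumed goals and show only how the rule behaves. For hypertension, what remains is a clarification of the type of goal and the listing of systolic values. The primary endpoint is not affected. The correction is cheap and should be made before unblinding.

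**What to change.** - **Outcomes, protocol and SAP:** score bradycardia in every patient against one uniform heart-rate threshold, fixed before unblinding and used for scoring only. The protocol's 50/min entry limit is one available value, but the team may choose another: with that limit, a patient entering at 51/min becomes an event after a fall of 2 beats. Report the goal-based version beside it, only for patients for whom a heart-rate goal was set, with that denominator shown.
- **SAP, Data Collection:** add heart rate and any heart-rate goal.
- **Consistency:** reconcile Subject Selection, both Outcomes sections and Data Collection, so that the two uses of the term bradycardia are clearly distinguished.
- **Hypertension:** list on-study systolic pressure, record whether each goal is systolic or mean, and apply the 20 percent systolic rule only to systolic goals. A second rate against one fixed systolic limit is an optional sensitivity analysis.

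The cost is some wording, a few form fields and two versions of the bradycardia rate to report. These are scoring rules, so no treatment rule changes.

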### Data Collection

Baseline descriptive data collection will occur on day of enrolment and includes age, sex, ethnicity, APACHE II score, admission diagnosis, pre-existing co-morbidities (diabetes, coronary artery disease, asthma, peripheral vascular disease, renal failure, psychiatric disease, musculoskeletal disease, and others) obtained from the subject, the subject's family, and the subject's medical chart. Baseline laboratory data will be recorded (haemoglobin, white cell count, alanine aminotransferase (ALT), international normalised ratio (INR), bilirubin, urea, creatinine, troponin, lactate). During the study daily SOFA scores, blood pressure goals, total fluid balances, transfused red blood cell units, administered corticosteroids, use of epidural analgesia, vasopressor and study drug start and end

times will be recorded. Days between admission and discharge from the ICU and hospital will be recorded. Readmissions to the ICU during the hospital stay will be identified through daily medical record review.

### **Sample size estimation**

The sample size estimation is informed by the previous observational study by Levine et al. In this study, the rates of vasopressor administration decreased by 38% from  $-0.62 \pm 1.40$  mcg/min per hour to  $-2.20 \pm 2.45$  mcg/min per hour after addition of midodrine. Based on a median time of 17 h from midodrine initiation to discontinuation of IV vasopressors, the 38% reduction translates to an estimated 6 h difference. 6 h is also thought to be a meaningful time frame in terms of reduction in duration of vasopressor treatment. Accordingly, we expect that a sample size of 50 subjects per group will provide us with >80% probability (power) to detect a difference of 6 h in the primary outcome. Allowing for drop-out, our target sample size is 120.

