### **Statistical analysis**

The study analysis will be performed on a modified intention-to-treat basis: All patients who were randomised and received at least 1 dose of the study medication will be included in the analysis.

Baseline and demographic characteristics will be presented using descriptive statistics. Continuous data will be expressed as means and standard deviations, or medians and interquartile ranges (IQR), depending on variable distribution. The normality of variable distribution will be assessed by exploratory data analysis, including histograms and boxplots. Differences in continuous data between groups will be assessed using a parametric t-test or Mann-Whitney U test, as appropriate. Categorical data will be presented as frequencies and proportions and analysed using a Chi-square test. If expected cell counts are small (less than 5), Fisher's exact test will be used instead. For all analyses, a two-sided p-value of less than 0.05 will be considered statistically significant. All analyses will be conducted under the supervision of a statistician blinded to intervention group assignment. Experienced study staff will perform data analysis in collaboration with biostatisticians using statistical Stata version 13 (StataCorp LLC, College Station, TX) or later.

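### The 38% behind the 6 h target does not follow from the slopes it is attached to, the arm of the 17 h median is not stated, and the power above 80% cannot be reproduced

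*Combined protocol and SAP*

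**What the plan says.** The SAP section Sample size estimation takes its figures from one cited observational study. It reports that "the rates of vasopressor administration decreased by 38" per cent, from -0.62 (SD 1.40) to -2.20 (SD 2.45) mcg/min per hour, once midodrine was added. It then converts this to hours: given "a median time of 17 h from midodrine initiation to discontinuation of IV vasopressors, the 38% reduction translates to an estimated 6 h difference". It adds a second ground for the target: "6 h is also thought to be a meaningful time frame in terms of reduction in duration of vasopressor treatment". From there it states that "a sample size of 50 subjects per group will provide us with >80% probability (power) to detect a difference of 6 h", and ends: "Allowing for drop-out, our target sample size is 120".

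Other inputs stand elsewhere in the SAP. Randomisation gives 1:1 allocation. Statistical analysis sets the level: "For all analyses, a two-sided p-value of less than 0.05 will be considered statistically significant". The same section leaves the test open: "Differences in continuous data between groups will be assessed using a parametric t-test or Mann-Whitney U test, as appropriate". The section on analysis of primary and secondary outcomes repeats that choice for the primary endpoint. Under Outcomes the primary endpoint is "measured in hours from initiation of midodrine until discontinuation of IV vasopressors", a wording that serves both arms.

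**The concern.** The stated reasoning runs from 38% to 6 h, and from 6 h to power above 80% with 50 per group. It is the only quantitative basis given for 100 evaluable patients, and the protocol's Study Design section ties the 120 to the same 6 h. The first step does not compute as written. The second depends on which arm the 17 h describes, and this is not said. The third cannot be checked. What is at stake is the reading of the result: if the trial finds no significant difference, readers will ask what difference it could have detected, and this section cannot tell them.

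**Working it through.** **Inputs from the documents.** Slopes -0.62 and -2.20 mcg/min per hour, 38%, median 17 h, target 6 h, 50 per group, total 120 (all from Sample size estimation); two-sided 0.05 and t-test or Mann-Whitney (Statistical analysis); 1:1 (Randomisation). **Not given:** an SD, IQR or distribution of the primary endpoint in hours, and the test to which the power refers. Every SD and shape below is therefore an assumption.

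**Step 1: the plan's 6 h.** 0.38 × 17 = 6.46 h, stated as 6 h. This reproduces once 38% is accepted and 17 h is taken as the untreated time.

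**Step 2: 38% against the slopes.**
- Ratio: 2.20 / 0.62 = 3.55.
- Relative change: (2.20 - 0.62) / 0.62 = 255% steeper.
- Inverse ratio: 1 - 0.62 / 2.20 = 72%.

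None of these is 38%. The slopes also became steeper, which a decrease of 38% does not describe.

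**Step 3: the arm of the 17 h.**
- 17 h untreated, 38% reduction: 17 × (1 - 0.38) = 10.5 h, difference 6.46 h.
- 17 h treated, 38% reduction: 17 / (1 - 0.38) = 27.4 h untreated, difference 10.4 h.
- 17 h treated, difference 6 h: 23 vs 17 h, and 6 / 23 = 26%.

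A time counted from midodrine initiation, in a study that added midodrine, reads most naturally as a treated time. Because the SAP counts its own endpoint from midodrine initiation in both arms, the wording does not settle the matter.

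**Step 4: power by t-test** (two-sided 0.05, mean difference 6 h). At 50 per group, 80% power needs a standardised difference of 0.566, so the SD can be at most 6 / 0.566 = 10.6 h. At 60 per group (120 / 2, no losses) the figures are 0.516 and 11.6 h.

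| Assumed SD (h) | 50 per group | 60 per group |
|---|---|---|
| 10 | 84% | 90% |
| 12 | 70% | 77% |
| 15 | 51% | 58% |
| 20 | 32% | 37% |

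The slope SDs do not explain the 50. With difference 1.58 and pooled SD √((1.40² + 2.45²) / 2) = 2.00, 80% power needs only 26 per group, and 50 per group gives 98%.

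**Step 5: power by Mann-Whitney** (simulation, both arms of the same shape with the medians shown, no censoring; accurate to about a point).

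| Medians (h) | n per group | Exponential | Weibull, shape 1.5 | Lognormal, log-SD 0.7 | Weibull, shape 2 |
|---|---|---|---|---|---|
| 17 vs 11 | 50 | 46% | 79% | 85% | 95% |
| 23 vs 17 | 50 | 25% | 49% | 55% | 73% |
| 38% kept: 17 vs 10.5, or 27.4 vs 17 | 50 | 53% | 86% | 91% | 98% |
| 17 vs 11 | 60 | 53% | 86% | 91% | 98% |
| 23 vs 17 | 60 | 29% | 57% | 63% | 80% |
| 38% kept, either arm | 60 | 61% | 91% | 95% | 99% |

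With both arms of the same shape, power depends only on the ratio of medians. If the 38% is kept, that ratio is 0.62 (that is, 1 - 0.38, not the slope) on either reading, so the arm makes no difference. If 6 h is held fixed, the ratio is 11/17 = 0.65 or 17/23 = 0.74, and the arm moves power by 21 to 31 points at 50 per group, depending on the shape.

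A t-test on the same simulated data at 50 per group gives 56/87/78/98% for 17 vs 11 h and 31/59/48/81% for 23 vs 17 h. The unstated test thus moves power by -7 to +10 points relative to Mann-Whitney.

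**The case against.** The best defence has four parts.

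- **The 38% may be a compressed citation.** It could measure some other quantity in the cited study, which is not available here. That stands: the documents show that the sentence contradicts its own figures, not that 38% is wrong in the source.
- **The 6 h target does not depend on the derivation.** The SAP also calls 6 h clinically meaningful, and the protocol uses 6 h consistently. That stands, and the target is not disputed. A clinical ground supplies no SD, however, so it cannot support a power figure.
- **Much of the calculation is stated or sound.** Alpha, allocation and two candidate tests are given, and 0.38 × 17 does give about 6 h. Taken alone, the missing SD and test would be missing detail. What makes this more than that is the inconsistent figure at the start of the reasoning.
- **Low power values come from chosen shapes.** No document figure supports any of the four. With the 38% kept, three of the four exceed 80% at 50 per group. That also stands, and is why the range is shown for all three pairs of medians.

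Two stronger readings are tempting. A reader might infer that the trial is underpowered. The documents do not support this, because without an SD or distribution in hours the power may lie on either side of 80%. If 17 h is a treated time and 38% holds, the expected difference is 10.4 h and 6 h is the more cautious target. A reader might also apply the slope ratio to the 17 h and conclude that the difference should be something quite different from 6 h. The SAP makes no such conversion, and the slopes are means with SDs larger than the means, so their ratio does not give a ratio of individual weaning times.

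**Conclusion.** The justification is wrong as written at its first step: slopes that differ 3.55-fold are described as a 38% change, and that 38% is the source of the derived 6 h. The second step is valid only if 17 h is an untreated time, which the SAP does not say. The stated power cannot be reproduced, and it is not shown to be below 80%. It holds by t-test if the SD is at most about 10.6 h at 50 per group. By Mann-Whitney it holds for two of the four assumed shapes at 17 vs 11 h, for none at 23 vs 17 h, and for three if the 38% reduction is kept. Which arm the 17 h belongs to matters for power only if 6 h is held fixed.

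The arithmetic on the slopes and hours rests on the SAP's figures alone. The power ranges rest on assumed SDs, on assumed shapes common to both arms, and on complete uncensored data. This is a defect in the stated basis for the sample size. It is worth correcting, but it is not evidence against the sample size itself.

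**What to change.** In the SAP's Sample size estimation section:

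1. Correct the 38% and its link to the slopes by saying what it measures, or remove it.
2. State which arm the 17 h median represents.
3. Rest the 6 h target on the clinical-relevance ground already given there.
4. Replace the statement of more than 80% with the power recalculated at 50 and 60 per group, from a stated SD or distribution in hours, naming its source and the test used.

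The cost is a few sentences and one calculation. Enrolment, endpoint and conduct do not change. The downside is that the stated power may become less favourable.
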